## **The impact of nurse-led programme with and without statin treatment base on traditional cardiovascular risk score or carotid ultrasound on addressing cardiovascular risk in patients with arthritis: a prospective, multicentre, randomised, controlled trial**

### **Introduction:**

Cardiovascular disease (CVD) risk is elevated in patients with rheumatoid arthritis (RA) and psoriatic arthritis (PsA) compared with the general population, and is a major source of morbidity and mortality (1, 2). New evidence strengthens the notion that the excess risk of CVD morbidity and mortality in patients with RA is related to both traditional and novel CVD risk factors. In RA, novel risk factors include inflammation, presence of carotid plaques, anticitrullinated protein antibody (ACPA) and rheumatoid factor (RF) positivity (3). In PsA, the prevalence of traditional risk factors is elevated compared with the general population, probably because of the shared inflammatory pathway (4).

CVD risk assessment is recommended for all patients with RA and PsA at least once every 5 years, so that lifestyle advice and CVD preventive treatment can be initiated when indicated (5). Current CVD risk prediction models, for example, Framingham Risk Score (FRS) or the Systematic COronary Risk Evaluation (SCORE) algorithm have been developed for use in the general population. Their performance in patients with RA appears to be suboptimal (6). Therefore, it has been suggested that CVD risk algorithms based solely on traditional risk factors may not be suited for use in the RA population. As a first step towards more accurate CVD risk prediction, it was proposed in the European League Against Rheumatism (EULAR) recommendations for CVD risk management in RA to apply a multiplication factor of 1.5 to the calculated CVD risk by SCORE (modified SCORE [mSCORE]) in selected patients to enhance the risk estimates (7). Nonetheless, a recent study showed that mSCORE do not provide sufficient improvement in risk prediction of future CVD in RA to serve as an appropriate alternative to the original SCORE (8).

Using coronary computer tomography angiogram (CCTA), we and others have found that all types of coronary plaque were more common in RA and PsA patients compared with controls, highlighted the fact that most of these subjects with plaques are having silent ischemia, supporting the notion that more aggressive CV evaluation strategy should be considered in these patients (9, 10). Nonetheless, there are concerns regarding costs and radiation exposure using CCTA or even coronary artery calcium (CAC) as a screening tool. Carotid ultrasound is a noninvasive imaging technique which can identify the presence of carotid plaque and increased intima-media thickness (IMT), representing an unequivocal manifestation of atherosclerosis and serving as a surrogate for CV disease. Other than carotid ultrasound, non-invasive pulse tonometry examination by measuring pulse wave velocity (PWV) and augmentation index (Alx) could evaluate overall aortic stiffness, which is an independent predictor of cardiovascular risk (11). Subclinical carotid atherosclerosis been shown to be more prevalent in RA (12) and PSA (13) then controls, even without classic CV risk factors. Increased IMT significantly correlated with traditional risk factors and disease-related parameters (12, 13).

Screening for asymptomatic atherosclerotic plaques by use of carotid ultrasound has been recommended as part of the CVD risk evaluation in patients with RA (5) as the presence of carotid plaques is associated with poor CVD-free survival and is strongly linked to future acute coronary syndrome (ACS)(14). The presence of bilateral plaque quadrupled the incidence of new ACS independently of any other risk factors compared with patients without carotid plaque (15). Incorporation of carotid ultrasound for patients at intermediate risk for CV disease has been used to further enhance CV risk stratification in the general population (16). Studies have supported the role of carotid ultrasound in re-stratification of CV risk. In RA, severe carotid ultrasound abnormalities were observed in 13% and 63% of patients with low and moderate mSCORE respectively (17). In PSA, our previous study showed that 35% of patients had subclinical atherosclerosis despite having a FRS-based low to moderate CV risk (13). Another study from Toronto also showed that 55.9% of the PsA patients from the FRS-based intermediate risk category were reclassified into an ultrasound-based high-risk category, while 47.1% of the patients in the FRS-based low-risk category were reclassified into a higher US-based risk group (18). Screening this population may help to identify those patients who are optimal candidates for intensive medical treatment. Prior studies suggest that incorporation of carotid ultrasound into treatment algorithms can impact progression of plaque and CV outcomes (19). However, the general applicability of these findings in rheumatology or primary care clinic

settings is not clear. Furthermore, guidelines on the management of patients with identified carotid plaque in RA and PsA have not been formulated.

Despite demonstration of high CV risk by the presence of carotid plaque, implementation of preventive CV services and rates of statin and antiplatelet use in PsA remained low in a recent study (20). "Best practice" electronic referrals were not an effective strategy to increase rates of specialty CV screening, even with a preventive cardiology clinic available in the same institution. It is possible that demonstration of carotid plaque can improve risk stratification but will only be impactful if incorporated into treatment plans by the treating rheumatologists as recommended by EULAR (5).

In RA patients, comorbidities are more common, more severe and less well-managed than in the general population (21). The usefulness of a nurse-led programme for decreasing CV risk has already been shown in a recent study. A single visit with a nurse might facilitate the management of risk factors of CVD by the general practitioner and/or the rheumatologist and demonstrated short-term benefit of a nurse-led programme on RA comorbidity management (22). However, whether the program resulted in changes of surrogate marker of CV endpoint (eg, glycaemia for diabetes, blood pressure for hypertension) remained uncertain because of its short study duration.

In addition to clinical screening, recent studies showed that various biomarker like calprotectin might play a role in detecting subclinical atherosclerosis, which calprotectin was associated with aortic PWV and presence of carotid plaque (23, 24). Our previous study also revealed that miRNA targeting IL-33 gene was associated with presence and progression of subclinical atherosclerosis .

**Aim and hypothesis:** We hypothesize that CV risk stratification and management in RA and PsA may be improved by incorporation of carotid ultrasound to assess for carotid plaque. This study investigates the impact of a nurse-led programme and initiation of statin treatment decided base on result of traditional CV risk score or carotid ultrasound on CV risk factor control in asymptomatic RA and PsA patients.

## **Patients and Methods**

### Subjects

#### *Inclusion criteria*

One hundred and forty consecutive patients with RA fulfilled the 2010 ACR/EULAR classification criteria or PsA fulfilled the Classification of Psoriatic Arthritis (CASPAR) criteria attending the outpatient clinics of the Prince of Wales Hospital who are aged between 18 and 75 will be recruited.

#### *Exclusion criteria*

Patients will be excluded if they have any one of the followings: a history of overt CVD (ie, symptomatic coronary artery disease [CAD] or ischemic stroke or transient ischemic attack or peripheral vascular disease), had significant co-morbidities including severe renal impairment or severe deranged liver function, female of childbearing potential who are unwilling to use adequate contraception, pregnant or breastfeeding women, and patients who are already taking lipid lowering therapy.

### Nurses

Rheumatology nurses will conduct the nurse-led clinic in Prince of Wales Hospital.

### Treating rheumatologists

Treating rheumatologists will invite their patients to participate in the study and will be responsible for managing patients with specific instructions given as listed below. Referred patients will then undergo formal screening by the research assistant for interest in the project and eligibility.

### Trial design

This is a 1-year prospective, hospital-based, open-label, randomized, controlled trial. The trial comprised two arms. Both group will participate in the nurse-led programme on CV risk screening and carotid ultrasound for carotid plaque assessment. Subjects in group 1 will initiate statin treatment if their Framingham Risk Score >10%; while subjects in group 2 will initiate statin treatment if they had carotid plaque upon carotid ultrasound findings.. (Appendix 1). The method of concealed random allocation will

be used. Simple randomization will be conducted by a computer-generated random list. Randomisation will be centralized for all centres. Information on each patient's allocated treatment will be recorded in the clinical report form (CRF) and also entered into the patient's computerized medical record (CMS) by the nurse. The study will be approved by the respective Ethics Committees of each hospital and all patients will provide written consent.

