#### Intervention of CV risk in the nurse-led clinic

All patients will receive a one-on-one nurse-led intervention at baseline and month 12 including:

- (1) Detection of CV risk factors (eg, hypertension, diabetes, hypercholesterolaemia).
- (2) Calculation of the FRS. We will follow the recommendation to adapt for patients with RA by a 1.5 multiplication factor (5).
- (3) The implementation of the recommendation for the detection (eg, yearly evaluation of CV risk factors) and/or management of such comorbidities at baseline. Nurses will be given a booklet to be used for the systematic identification and assessment of the comorbidities associated with RA and PsA. In case of a detected risk factor (eg, hypertension) and/or a non-optimally managed comorbidity (eg, Hba1c > 7), the nurse reminds the patient the interest of the management of such comorbidity and advises the patient to visit her/his general practitioner and/or rheumatologist to take care of it. In parallel, a report of this visit will be given to the patient to hand-over to the rheumatologist of each evaluated patient during their next clinical visit.
- (4) The report of the presence of newly developed CV comorbidities at month 12.
- (5) The number of new measures taken against comorbidities at month 12. The following measures against comorbidities are considered for the definition of the secondary objective of the trial: purchase of BP self-measurement devices, attending education class by dietitian and initiation of a diet because of overweight +/- hyperlipidemia, smoking cessation, initiation of lipid-lowering therapy, initiation of antiplatelet therapy, referral to a nephrologist because of renal insufficiency (chronic kidney disease stage IIIb).
- (6) adherence of lipid-lowering and antiplatelet therapy at month 12.

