**Statistical analysis:**

Descriptive statistics will be used for demographic and clinical variables included frequencies, percentage, means and standard deviations, median and interquartile range. Comparisons in demographic and clinical characteristics at baseline will be performed using chi-square test, independent samples *t*-test or Mann-Whitney *U* test, depending on distribution of data. We will compare the proportion of participants eligible for statin treatment using FRS >10% vs carotid ultrasound criteria using the McNemar test. The intervention effect on the primary and secondary outcomes will be examined at 12 months on an intention-to-treat basis using a mixed-effects regression model adjusted for baseline FRS. The model will also take into account random effects associated with physicians and clinics in a hierarchical structure. The magnitudes and patterns of missing data will be examined by the randomized group. Missing outcomes at the 12-month follow-up will be imputed using the method of the baseline observation carried forward. The same mixed-effects model will be used for subgroup analyses defined by sex and underlying diseases. All statistical analyses will be conducted using IBM SPSS Statistics Version 23 (IBM, Armonk, NY, USA). A level of significance of *p* =0.05 is used.

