**Sample size calculation:**

The sample size is estimated by the Power Analysis and Sample Size for Windows software (PASS 2000, NCSS, Utah, USA). All calculations will use a two-sided  $\alpha$  of 0.05 and  $\beta=0.2$  achieving 80% power. From our previous cohort study, standard deviation of FRS was 8. Taking population variance of FRS as 64, and suppose 4 unit drop in FRS is clinically meaningful. A sample size of 63 is required in each group. Assuming a drop-off rate of 10%, a total sample size of 140 (i.e. 70 per arm) would be sufficient.

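### Simple randomisation of 140 patients leaves arm sizes and RA/PsA balance to chance; blocking the existing central list by disease is a modest gain at almost no cost

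*Protocol*

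**What the plan says.** Under Trial design, "The trial comprised two arms", and "Simple randomization will be conducted by a computer-generated random list". The same section adds: "Randomisation will be centralized for all centres". Allocation is described as concealed, and the trial is open-label. Blocking, stratification and minimisation are not mentioned.

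The sample size section derives 63 evaluable patients per group, allows for 10% drop-off, and concludes that "a total sample size of 140 (i.e. 70 per arm) would be sufficient".

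Three other places bear on disease:

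- The section on the nurse-led clinic says the FRS calculation will follow a recommendation to "adapt for patients with RA by a 1.5 multiplication factor". No factor is given for PsA.
- Outcome measures makes change in FRS the primary outcome and does not mention the factor.
- Statistical analysis adjusts the mixed model for baseline FRS, with random effects for physicians and clinics. It plans to use the same model for "subgroup analyses defined by sex and underlying diseases". Disease is not named as a covariate in the main analysis.

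Inclusion criteria admits RA or PsA patients without a quota for either.

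**The concern.** An unrestricted list secures neither equal arms nor a similar disease mix in each arm. Disease plausibly matters here. It defines a planned subgroup, and it sets the scale of the FRS as calculated in the nurse clinic. If the 1.5 factor carries into the primary outcome, it also scales the measured change.

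A chance difference in RA share could then move the between-arm comparison slightly and leave a disease subgroup unevenly split. The choice of list is made in the protocol and cannot be undone by a later analysis plan once patients are allocated. A central computer-generated list already exists and diagnosis is known at eligibility, so restricting the list needs no new data.

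**Working it through.** **1. The plan's own figure.** Inputs from the sample size section: difference 4, SD 8, two-sided alpha 0.05, power 80%.

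n per arm = 2 × (1.960 + 0.842)² × 8² / 4² = 62.8, so 63. Dividing by 0.9 for drop-off gives 63 / 0.9 = 70 per arm, 140 in total. The stated figures reproduce.

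**2. Arm sizes under simple randomisation.** The size of one arm is Binomial(140, 0.5).

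- SD = √(140 × 0.25) = 5.9; 95% range 58 to 82.
- P(exactly 70:70) = 6.7%.
- P(smaller arm is 62 or fewer, before any drop-out) = 20.5%.
- P(smaller arm is below 60) = 7.6%.

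**3. Power cost.** With 10% loss in each arm, SE = 8 × √(1/(0.9 n₁) + 1/(0.9 n₂)) and power = Φ(4/SE − 1.960).

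| Randomised | SE | Power |
|---|---|---|
| 70:70 | 1.43 | 80.1% |
| 63:77 | 1.43 | 79.7% |
| 60:80 | 1.44 | 79.3% |
| 58:82 | 1.45 | 79.0% |

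Averaged over all splits, power is 79.8%. The cost is about 0.3 points on average and about 1.2 points at the 95% limit.

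**4. Balance on disease.** The protocol fixes no RA share, so 30%, 50% and 70% are assumed. RA and PsA patients are each allocated by fair coin, and the RA share is compared between arms.

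| RA share (assumed) | SD of difference | P(difference ≥ 10 points) | P(difference ≥ 15 points) |
|---|---|---|---|
| 30% or 70% | 7.8 points | 20.5% | 5.3% |
| 50% | 8.5 points | 27% | 7.6% |

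A disease subgroup of 70 has a 95% range of 27 to 43 in one arm; a subgroup of 42 has 15 to 27. Relative to an even split, a 27:43 split keeps 4 × 27 × 43 / 70² = 95% of the efficiency.

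**5. Effect on the primary estimate, if the 1.5 factor enters the outcome.** The factor adds 0.5 times the unscaled value in each RA patient. A 10-point difference in RA share therefore shifts:

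- mean baseline FRS by 0.10 × 0.5 × 10 = 0.5 units for an assumed mean unscaled FRS of 10 (0.25 to 0.75 for means of 5 to 15);
- mean FRS change by 0.10 × 0.5 × 1, 2 or 4 = 0.05, 0.10 or 0.20 units for assumed mean unscaled changes of 1, 2 or 4.

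The target difference is 4 and the standard error is 1.43. Baseline adjustment removes part of even these shifts.

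**6. What a disease term adds to the model.** Suppose disease shifts FRS change by δ beyond what baseline FRS explains, with half the patients RA and the plan's SD of 8 as the total. Disease then accounts for 0.25 δ² of the variance of 64.

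- δ = 2: 1/64, so the SD falls by 1 − √(1 − 1/64) = 0.8%.
- δ = 4: 4/64, so the SD falls by 3.2%.
- A 9% gain needs δ of about 6.6 (0.25 × 6.6² = 10.9; 1 − √(1 − 10.9/64) = 0.09).

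Where disease acts only through the FRS scale, simulation of 140 patients (half RA, assumed baseline mean 10, unscaled change SD 5) gives a precision gain of about 0% to 2% from stratifying and adding the term.

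**The case against.** Simple randomisation is a legitimate choice. It is unbiased, the test and interval already allow for chance imbalance, and it is the least predictable scheme for an open-label trial. All of that stands.

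A reader might go further and infer that the protocol contradicts itself by promising 70 per arm and then using a method that seldom gives it. The documents do not support this. The 70 is a planning figure and the expected split of a 1:1 list, and nothing promises an exact 70:70. Nor do they support reading the uneven arms as a material loss of power.

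A reader might also infer that disease sets the scale of the primary outcome. The factor appears only in the description of the nurse-clinic calculation, and whether it carries into the outcome is not stated. If it does, baseline FRS carries the same factor, so the planned adjustment absorbs most of the effect. The share of patients above the FRS trigger is a dichotomy of that same covariate, so a separate FRS stratum would add little.

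Finally, comparisons within a disease subgroup remain randomised, and a moderately uneven split costs little efficiency. Extra covariates may also be set out in an analysis plan that is not shown.

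What survives is narrower: the type of list is fixed in the protocol, and a better one is available at almost no cost.

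**Conclusion.** The point holds as a modest design improvement. It is not an error in the sample size, a source of bias, or a threat to power.

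The method leaves about a one in four or five chance of a 10-point or larger difference in RA share. That rests on an assumed RA share between 30% and 70%. The likely effect on the primary estimate is small beside the target of 4 units. It becomes noticeable only if disease has its own sizeable effect on FRS change, which the protocol neither states nor rules out. The more secure benefits are predictable arm sizes and evenly split disease subgroups.

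**What to change.** Generate the same central, concealed list in permuted blocks of randomly varying size, stratified by RA/PsA. Add disease as a fixed covariate in the primary mixed model. No FRS stratum is needed, because baseline FRS is already a covariate.

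As an illustration, with blocks of 4 and two strata the arms differ by at most 2 patients per stratum. The worst overall split is then 68:72, with power after 10% loss of 80.1%. N stays at 140.

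The cost is a regenerated list and one model term for a variable already collected. The downside is slightly more predictable allocation in an open-label trial, limited by the varying block sizes and central concealment. If enrolment has begun, keep the list and pre-specify the disease covariate alone.

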#### Clinical assessment

At baseline and then every 3 to 6 months up to 1 year, the following clinical variables and questionnaires will be assessed: erythrocyte sedimentation rate (mm/h1st), CRP (mg/L), number of swollen joints (0–28 for RA, 0-66 for PsA), number of tender joints (0–28 for RA, 0-68 for PsA), number of damaged joints, visual analogue scale (VAS) for pain (0-10=most pain), VAS for patient's global assessment (0-10=worst score), and VAS for physician's global assessment (0-10=worst score). Functional disability will be assessed by the disability index of Health Assessment Questionnaire (HAQ) (0-3=most functional disability). Overall disease activity will be assessed using 28-joint assessment (DAS28) for established RA (symptom onset greater than 2 years), simplified disease activity score (SDAI) for early RA (symptom onset less than 2 years), and Disease Activity in Psoriatic Arthritis (DAPSA), Bath Ankylosing Spondylitis Functional Index (BASFI) Test and Bath Ankylosing Spondylitis Disease Activity Index (BASDAI) for PsA. Quality of life outcome will also be assessed at baseline and month 12 by Short Form (36) Health Survey and EQ5D. PsA patients will also complete the Dermatology Life Quality Index (DLQI) and Ankylosing Spondylitis Quality of Life (AsQoL) questionnaire.

#### Cardiovascular assessments

The following anthropomorphic assessment will be performed for all patients at baseline and at the end of the study. Anthropomorphic measurements include body heights, body weight, waist and hip circumferences, two consecutive blood pressure (BP) readings in sitting position and heart rate. Hypertension status is defined as systolic blood pressure (SBP)  $\geq 140$  mmHg or diastolic blood pressure (DBP)  $\geq 90$  mmHg or the use of antihypertensive agents. Other data collected at baseline include menopausal status, smoking and drinking habits, social economic status, history of diabetes, hypertension, hypercholesterolemia, dyslipidemia, overt CVD and cerebrovascular diseases, peptic ulcer disease and family history of CVD, diabetes and cerebrovascular diseases in first-degree male relatives  $< 55$  years of age or first-degree female relatives  $< 65$  years of age. Drug history is retrieved from case notes or elicited during the clinical assessment. Body weight and blood pressure will also be measured during each visit to the rheumatologist.

Laboratory assessment at baseline include fasting blood glucose, fasting lipid profile (total cholesterol [TC], low-density lipoprotein-cholesterol [LDL-C], high-density lipoprotein-cholesterol [HDL-C], triglycerides [TG]), fibrinogen, thyroid function test, creatinine kinase and uric acid. Fasting sugar and lipid profile will also be measured at 6 and 12 months. Hemoglobin A1c levels will be measured at baseline and 12 months for patients with known diabetes.

#### Rationale for choosing FRS and the level of cut off for intervention

Evidence is scarce with regard to the validity of disease specific CVD risk prediction models to accurately predict risk in individual patients with RA and PsA, and it is therefore currently recommended to perform risk evaluation according to general population guidelines. Currently, no national guideline is available in Hong Kong. In our previous study to evaluate the performances of different CV risk scores in detecting high CV risk in PsA patients identified by coronary plaques on CCTA, we categorized patients as having either low or elevated 10-year CV risk using the 10% threshold for the FRS and found that FRS provided better discrimination of PsA patients with significant coronary artery plaque on CCTA than 3 other commonly used risk scores (25). Therefore, FRS was chosen to predict CV risk and a cut off of 10% was chosen to identify high risk individuals for interventions such as lipid-lowering treatment.

